11.2 Serious Adverse Experiences (SAE)

An SAE is defined as any AE occurring at any dose that results in any of the following outcomes:

- death
- a life-threatening adverse experience
- inpatient hospitalization or prolongation of existing hospitalization
- a persistent or significant disability/incapacity

- a congenital anomaly/birth defect

Other important medical events may also be considered an SAE when, based on appropriate medical judgment, they jeopardize the subject or require intervention to prevent one of the outcomes listed.

11.2.1 Serious Adverse Experience Reporting

The study site will document all SAEs that occur (whether or not related to study drug) per [UCSF CHR Guidelines](#). The collection period for all SAEs will begin after informed consent is obtained and end after procedures for the final study visit have been completed.

In accordance with the standard operating procedures and policies of the local Institutional Review Board (IRB)/Independent Ethics Committee (IEC), the site investigator will report SAEs to the IRB/IEC.

11.3 Protocol Defined Important Medical Findings Requiring Real Time Reporting

The following medical findings that occur will require real time reporting by the inpatient surgical team to the medical monitoring team:

- Cardiovascular: Bradycardia, Heart Block, Ventricular Arrhythmia, and/or Cardiac Arrest requiring intervention
- Neurologic: Seizure
- Hypersensitivity: Anaphylaxis
- Death

12 DISCONTINUATION AND REPLACEMENT OF SUBJECTS

12.1 Early Discontinuation of Study Drug

Early discontinuation of study drug is not applicable as study drug is given in a single episode.

12.3 Withdrawal of Subjects from the Study

A subject may be withdrawn from the study at any time if the subject or the investigator feel that it is not in the subject's best interest to continue.

All subjects are free to withdraw from participation at any time, for any reason, specified or unspecified, and without prejudice.

Reasonable attempts will be made by the investigator to provide a reason for subject withdrawals. The reason for the subject's withdrawal from the study will be specified in

the subject's source documents. Subjects who withdraw after Visit 2 but prior to Visit 3 will be encouraged to come in for a final visit.

12.4 Replacement of Subjects

Subjects who withdraw from the study treatment will be replaced.

13 PROTOCOL VIOLATIONS

A protocol violation occurs when the subject or investigator fail to adhere to significant protocol requirements affecting the inclusion, exclusion, subject safety and primary endpoint criteria. Protocol violations for this study include, but are not limited to, the following:

Failure to meet inclusion/exclusion criteria

Did not receive specified intervention

Use of a prohibited concomitant medication

Failure to comply with Good Clinical Practice (GCP) guidelines will also result in a protocol violation. The sponsor will determine if a protocol violation will result in withdrawal of a subject.

When a protocol violation occurs, it will be discussed with the investigator and a Protocol Violation Form detailing the violation will be generated. This form will be signed by the Investigator. A copy of the form will be filed in the site's regulatory binder and in the Sponsor's files.

14 DATA SAFETY MONITORING

A Data Monitoring Committee (DMC) comprised of the Medical Monitor, External Investigator, and Clinical Pharmacist will review data relating to safety and efficacy, conduct and review interim analyses, and ensure the continued scientific validity and merit of the study, according to the UCSF Data Safety Monitoring Board Operations Manual and a DMC Charter to be established for this protocol. There will be an interim review conducted at 1/3 and 2/3 goal enrollment by the DMC for the purpose of monitoring study conduct and assessing patient safety. Further details regarding the timing and content of the interim reviews is included in the statistical section below.

14.1 DMC Charter

Introduction

The purpose of this charter is to define the responsibilities of the DMC, detail membership requirements, describe the data to be reviewed, delineate the meeting process, and outline the considerations and policies of the DMC. The DMC will act in an expert, independent advisory capacity to monitor participant safety, and evaluate the efficacy and conduct of the study.

Study Overview

- Study title: Minimally Invasive Thoracic Surgery Intercostal Nerve Block Trial
- Study design: Randomized, double-blind, active-comparator controlled clinical trial to assess the analgesic efficacy of intercostal nerve block by Liposomal Bupivacaine versus Standard Bupivacaine in subjects undergoing minimally invasive lung resection.
- Phase: III
- Number of participants: 80
- Number of sites: 1

DMC Responsibilities

- Review the research protocol, informed consent documents, and plans for data safety and monitoring prior to initiation of study, periodically during the study, and at the conclusion of the study;
- Conduct interim and final evaluation of the study, including safety data, quality and timeliness of data submission, participant recruitment, accrual and retention, risk versus benefit, including unanticipated problems and protocol violations, efficacy, statistical outcomes, and other factors that can affect study outcome, including aggregate and individual participant data related to safety, data integrity and overall conduct of the study;
- Protect the safety of the study participants;
- Review and evaluate ad hoc safety issues concerning the study at the request of the Investigator;
- Make recommendations to the Investigators concerning continuation, termination, or other modifications of the study based on the observed beneficial or adverse effects of the study;
- Operate according to the procedures described in this charter.

DMC Membership

The DMC will be comprised of an External Investigator, Clinical Pharmacist, and the Medical Monitor who will also serve as the Chairman of the DMC.

- External Investigator: [name], Assistant Professor of Surgery at UCSF. [name] is the Surgical Director of the Enhanced Recovery After Surgery Program in Colorectal Surgery and has expertise in postoperative analgesia.

- Clinical Pharmacist: [name] at UCSF. [name] has expertise pertaining to the efficacy and risks associated with local amide analgesia.

- Medical Monitor / Chairman of the DMC: [name] MD, Clinical Professor of Anesthesia at UCSF. [name] was selected as he is an expert in local amide analgesia.

Although DMC members are expected to serve for the duration of the study, in the unlikely event that a member is unable to continue participation, the reason will be documented and a replacement member will be selected by the Investigator. The new member must have comparable expertise and qualifications to the DMC member he/she is

replacing. DMC members must not have any real or perceived scientific, financial, professional, personal, proprietary, or other conflict of interest related to the conduct, outcome, or impact of the study.

Review of Safety Data

The primary charge of the DMC is to monitor the study for participant safety. The safety and related data the DMC will review includes,

- Participant recruitment, accrual, retention, and withdrawal information
- Adverse events (AEs) and serious adverse events (SAEs)
 - Tabulated by body system, intensity, seriousness, duration, treatment given, and the relationship to the study drug and study procedure
 - Comparison of events that occur between treatment arms
 - Individual events of particular concern

In particular, the following are adverse events of special interest pertinent to Liposomal Bupivacaine and Standard Bupivacaine:

- Nausea, emesis, and/or constipation and are expected to occur in >10% of subjects.
- Less common adverse events include dizziness, altered mental status, and hypersensitivity reactions with urticaria and/or pruritis.
- Very rare, but serious adverse events include neurologic toxicity with seizures and apnea, cardiac toxicity with atrioventricular nodal conduction abnormalities and cardiac arrest, and hypersensitivity reaction with anaphylaxis.

SAEs must be reported by the Investigator to the DMC Chair.

Review of Other Data

- Effectiveness

The DMC monitors effectiveness outcomes to determine relative risk/benefit, futility, or for early termination due to overwhelming effectiveness.

- Study Conduct

The DMC reviews data related to study conduct. Data to be reviewed and listed in the DMC reports regarding study conduct includes: summary of protocol violations, completeness and timeliness of study visit data, enrollment eligibility and ineligibility information, noncompliance, unanticipated problems, information concerning withdrawal of participants. The DMC may issue recommendations regarding study conduct when concerns arise that aspects of study conduct may threaten participant safety or study integrity.

DMC Meetings

- Projected Schedule of Meetings

An initial meeting of the DMC will be held prior to any participant enrollment in order for the members to review the charter, form an understanding of the protocol and definitions being used, establish a distribution and meeting schedule, review the study modification and/or termination guidelines, and finalize format and protocol-specified statistical

methods to be used in reports to be considered by the DSMB. Subsequent DMC meetings will be held to review at 1/3 and 2/3 goal enrollment, and at the conclusion of the study.

- Ad Hoc Meetings

An ad hoc meeting of the DMC may be called at any time if imminent participant safety issues arise. If a significant safety concern arises during the study, the DMC Chair may convene a meeting to review safety and any other aspect of the study. Significant safety events may include, but are not limited to, the following:

- A death or life-threatening condition sustained by a participant, regardless of causality
- An unexpected serious safety issue newly identified during the development program that could expose participants to unnecessary risks
- Any other concern regarding participant safety raised by any DMC member

- Meeting Format

DMC meetings will be conducted in person.

- Voting

DMC recommendations will be agreed upon by formal majority vote. In event of a split vote, the DMC Chair will cast the deciding vote.

- Stopping Rules

The DMC will determine whether the study should continue as planned, proceed with modifications, or be terminated. The justification to terminate the study may be due to the DMC's analysis that there is overwhelming effectiveness, futility, or safety issues. If the DMC votes to terminate the study, a final study report will be made.

15 STATISTICAL METHODS AND CONSIDERATIONS

Prior to the analysis of the final study data, a detailed Statistical Analysis Plan (SAP) will be written describing all analyses that will be performed. The SAP will contain any modifications to the analysis plan described below.

15.1 Data Sets Analyzed

All eligible patients who are randomized into the study and receive the intervention will be included in the analysis.

15.2 Demographic and Baseline Characteristics

The following demographic variables at screening will be summarized: age, gender, race and ethnicity, height, weight, comorbid conditions, smoking history, lung function, indication for surgery, prior thoracic surgery.

15.3 Analysis of Primary Endpoint

Null Hypothesis: There is no difference in cumulative in-hospital use of opioids in subjects who receive intercostal nerve block and wound infiltration Liposomal Bupivacaine or Standard Bupivacaine during minimally invasive lung resection.

Student's t-test will be used to assess the means of the cumulative total of in-hospital oral morphine equivalents. It is presumed that the data will be normally distributed. If this assumption is not met, transformation or nonparametric tests (Mann-Whitney U test) will be used. Moreover, as there are only 40 subjects per group, it is possible that we do not achieve effective randomization. If this occurs, we will utilize linear regression adjusting for age, sex, race, comorbidity, diagnosis, and procedure performed. A power of 0.8 and 2-sided alpha error set at 0.05 will be used to assess for statistical significance.

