| CONCOMMITANT MEDICATIONS | 
Allowed:
 
Standardized Hospital Pain Medication Regimen
 
All subjects will receive a standardized postoperative pain regimen. Goal pain management is to allow the subject to ambulate and perform incentive spirometry per standard care. Escalation of opioid dosing if needed will be at the discretion of the inpatient surgery team.
 
Standardized Discharge Pain Medication Regimen
 
All subjects to be discharged on a standardized pain regimen.
 
Prohibited:
 
None
 |
| EFFICACY EVALUATIONS | |
| PRIMARY ENDPOINT | 
 • Cumulative Daily In-Hospital Use of Opioids (morphine equivalents in mg) |
| SECONDARY ENDPOINTS | 
 • Cumulative Daily In-Hospital Pain Score (0-10) • Mean Time to First Opioid Use (hours) |

| | |
|---|---|
| | 
 • Mean Time to Ambulation (hours) • Pulmonary Complications (y/n) • Liposomal & Standard Bupivacaine Adverse Events (y/n) • Total Opioid Prescription at Discharge (morphine equivalents in mg) • Total Opioid Use as Outpatient (morphine equivalents in mg) • Length of Stay (days) • Direct Costs of Hospital Encounter (dollars) • Quality of Life: Short-Form-8 Health Survey |
| OTHER EVALUATIONS | n/a |
| SAFETY EVALUATIONS | 
 - All subjects will be monitored with continuous cardiac telemetry throughout the entirety of their hospitalization. - Nursing staff will assess the mental status of each participant at the start of each shift. - Surgical wounds will be monitored daily by the surgery inpatient team. - The minimum duration of inpatient monitoring is 24 hours. For subjects that are discharged on POD1 after 24 hours of monitoring, a safety assessment will be performed on POD2. - Adverse events will be assessed continuously, starting with the first patient enrollment and until study completion, and will be immediately reported to the Medical Monitor. - Serious and severe adverse events, regardless of causality, will be followed until resolution or stabilization. - Subjects will be discharged with specialized discharge instructions to alert them of potential adverse effects and instruct them when to call the clinic. |

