| PLANNED INTERIM ANALYSES | When the study has reached 1/3 and 2/3 goal enrollment, interim analysis for safety will be conducted by an independent data monitoring committee. Serious and severe adverse events will be monitored by the committee on an ongoing basis throughout the study. |
| STATISTICS Primary Analysis Plan & Rationale | 
Null Hypothesis: There is no difference in cumulative daily in-hospital use of opioids in subjects who receive intercostal nerve block and wound infiltration with Liposomal Bupivacaine or Standard Bupivacaine during minimally invasive lung resection.
 
Statistical Method: Student's t-test.
 
Rationale: 80 subjects will provide 80% power to detect a statistically significant effect with 2-sided alpha error set at 0.05 if the measured effect is 19% absolute reduction in cumulative daily in-hospital use of opioids.
 |

| | |
|--|---|
| | 
The mean cumulative daily in-hospital usage of opioids is 35mg morphine equivalents with standard deviation of 12mg. This was estimated by review of previously published studies and corroboration with UCSF clinical practice patterns. A 19% reduction in cumulative daily in-hospital use of opioids corresponds to 1 fewer oxycodone dose per day, which was considered clinically significant.
 |
|--|---|

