5 CRITERIA FOR EVALUATION

5.1 Primary Efficacy Endpoint

- Cumulative Daily In-Hospital Use of Opioids measured in mg of Oral Morphine Equivalents

The subjective sensation of pain is challenging to measure. Cumulative daily in-hospital opioid use measured in mg of oral morphine equivalents acts as a surrogate endpoint of pain and is commonly used in the literature. It provides objective data that are recorded on every subject in the medication administration record.

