15.6 Sample Size and Randomization

80 Subjects will be randomized to 1:1 to Liposomal Bupivacaine or Standard Bupivacaine by varying block size (4-8). 80 subjects will provide 80% power to detect a statistically significant effect with 2-sided alpha error set at 0.05 if the measured effect is 19% absolute reduction in cumulative daily in-hospital use of opioids.

The mean daily in-hospital usage of opioids is 35mg morphine equivalents with standard deviation of 12mg. This was estimated by review of previously published studies and corroboration with UCSF clinical practice patterns [12]. A 19% absolute reduction in cumulative daily in-hospital use of opioids corresponds to 1 fewer oxycodone dose per day, which was considered the minimum clinically significant effect.

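### The primary endpoint and sample size are on a daily opioid scale, but Section 15.3 tests an in-hospital total, and no section defines one value per subject

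*Combined protocol and SAP*

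**What the plan says.** Section 5.1 names the primary endpoint "Cumulative Daily In-Hospital Use of Opioids measured in mg of Oral Morphine Equivalents". The Synopsis uses the same daily label for the endpoint, and its null hypothesis reads "There is no difference in cumulative daily in-hospital use of opioids in subjects who receive intercostal nerve block".

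Section 15.6 sizes the trial on that scale: "The mean daily in-hospital usage of opioids is 35mg morphine equivalents with standard deviation of 12mg". The 19% target "corresponds to 1 fewer oxycodone dose per day, which was considered the minimum clinically significant effect".

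Section 15.3 is the operative analysis text and uses other words. Its null hypothesis is "There is no difference in cumulative in-hospital use of opioids in subjects who receive intercostal nerve block", without *daily*, and the Student's "t-test will be used to assess the means of the cumulative total of in-hospital oral morphine equivalents".

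Section 15 announces a detailed SAP, to be written before the final data are analysed: "The SAP will contain any modifications to the analysis plan described below".

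**The concern.** A t-test needs one number per subject, and the plan points to two. One is an amount per day; the other is an amount over the stay. Both sentences in Section 15.3 lack *daily*, and neither a window nor a per-day denominator replaces it.

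The difference matters because stay is not fixed. Section 5.3 gives only a 24-hour minimum for inpatient monitoring. Section 5.2 makes length of stay a secondary endpoint and says attending practice patterns limit it. Section 3.2 asks whether better analgesia shortens it. A stay total therefore mixes opioid need with discharge timing.

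Three things are at stake:

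- Analysts following Section 5.1 and Section 15.3 would test different variables and could reach different primary conclusions. The choice could also be made after the data are seen.
- The 35 and 12 mg planning figures do not describe a stay total, so the stated power does not apply to the test in Section 15.3.
- Section 15.5 sets a stopping boundary of |z| > 3 at one third and two thirds of enrolment without naming the variable behind z. If it is the primary endpoint, the definition is needed before the first interim review, earlier than the promised SAP is due.

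**Working it through.** **The plan's own figure.** Inputs from Section 15.6: mean 35 mg, SD 12 mg, 19% reduction, two-sided 0.05, 40 per arm. The difference is 0.19 × 35 = 6.65 mg per day, and the standardised effect is 6.65/12 = 0.554. Exact t-test power at 40 per arm is 68.7%, and 80% power needs 53 per arm (52.1 before rounding). The stated 80% is not reproduced. That is a separate problem; 69% is used here only as the daily benchmark.

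**Assumptions.** The documents give no stay data. Assumed: stay L is log-normal with mean 3 days and coefficient of variation c, independent of daily use D; D is normal with SD 12 and constant over the stay; 40 per arm.

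**Spread of the total, T = D × L.** CV(T)² = CV(D)² + c² + CV(D)²c², with CV(D) = 12/35 = 0.343. At c = 0.3 this is 0.1176 + 0.0900 + 0.0106 = 0.2181, so CV(T) = 0.467 and SD(T) = 0.467 × 105 = 49.0 mg on a control mean of 3 × 35 = 105 mg. A 19% reduction is 19.95 mg on this scale.

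**Constant daily use** (40,000 simulated trials per setting):

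| | c = 0.2 | c = 0.3 | c = 0.5 |
|---|---|---|---|
| SD of total, control arm (mg) | 42.3 | 49.0 | 66.2 |
| Rejection, no drug effect, equal stay | 4.9% | 4.9% | 4.8% |
| Power, daily use 19% lower, equal stay | 57% | 47% | 30% |
| Per arm for 80% power on the total | 69 | 90 | 155 |
| Rejection, daily use unchanged, stay 10% shorter in one arm | 21% | 17% | 11% |
| Rejection, daily use unchanged, stay 20% shorter in one arm | 68% | 56% | 34% |

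Analytic power for the third row is 56.7%, 46.2% and 29.2%. The assumed mean stay hardly matters: at c = 0.3, power is 47% for means of 2, 3 and 5 days.

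**Declining use.** Opioid use may fall over the stay. Let D be the first-24-hour total, normal with mean 35 and SD 12, let use halve every h days, and let stay be at least 1 day. Then T = D × (1 − 2^(−L/h)) / (1 − 2^(−1/h)), and mg per hospital day is T/L. With c = 0.3 and 20,000 trials:

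| | h = 1 | h = 2 | h = 3 |
|---|---|---|---|
| Stay 20% shorter, no effect on use: total | 16% | 32% | 40% |
| Same: mg per day | 35% | 18% | 12% |
| Power, use 19% lower, equal stay: total | 66% | 61% | 56% |
| Same: mg per day | 57% | 64% | 65% |

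A per-day mean is therefore not free of stay either. At a 1-day half-life it depends on stay more than the total does and has less power.

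**The case against.** The strongest reply is that the label itself joins *cumulative* to *daily*, so Section 15.3 may only be shorthand for a total per day, and the promised SAP is the natural place for the start time and denominator. The loose-wording reading is possible. It does not rescue the plan: a total per day still gives several values per subject, and no section says how they become one. A later SAP may correct the rule, but the rule now stated conflicts with the stated endpoint.

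A second reply is that moving Section 15.3 to a per-day mean prejudges the definition, when the declining-use figures show that such a mean can do worse than the total. This stands in part. The documents require one definition used throughout, and the window is for the sponsor to choose. Nor can it be claimed that 35 and 12 mg fit a stay average exactly. The units and daily scale match, but the documents do not show whether the SD is between subjects on a stay average, on one day, or pooled over days.

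Third, every stay input is assumed, including independence of stay and use, and the simulations use the t-test throughout although Section 15.3 allows a transformation or Mann-Whitney test for non-normal data. With Mann-Whitney, power on the total is about 48% at c = 0.3 and 34% at c = 0.5, against 47% and 30%. The direction is unchanged and the shift is small.

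**Conclusion.** The concern holds and should be corrected before any data are analysed. The primary variable is stated in two ways and fully defined in neither. That follows from the text alone and needs no assumption about stay.

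The consequences are illustrative. When stay is alike in both arms, the test on the total keeps its 5% error rate, so the harm there is lost power: 57% to 30% across the assumed range, against 69% for a daily measure, if daily use is constant. If use declines quickly the loss shrinks or reverses. When stay differs between arms, a significant total can reflect time in hospital rather than daily opioid need. A 20% difference produces that in 68% to 34% of trials under constant use, and in 16% to 40% under declining use at c = 0.3.

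**What to change.** 1. In Section 15.3, replace the stay-total wording with the daily endpoint of Section 5.1 and restore *daily* in the null hypothesis.
2. State one per-subject definition: start time, window or denominator, partial days and early discharge. Use it word for word in the Synopsis and Sections 5.1, 15.3 and 15.6. Mean mg per hospital day (the total from completion of the block to discharge, divided by days of stay) fits the units and scale of Section 15.6; the sponsor may choose another window.
3. Restate power with a mean and SD for that variable, and say where they come from.
4. Report the stay total as a secondary or sensitivity analysis. Because a per-day mean still depends on stay when use declines, add a fixed-window total, such as the first 24 hours, which the monitoring minimum in Section 5.3 makes observable in all subjects.

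The cost is wording in four places, one power calculation and one or two sensitivity analyses. Section 5.1 says the medication administration record already holds the data.

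The downside is that restated power may fall below 80%. It is 69% at the stated inputs. Suppose the 6.65 mg per day effect starts only after hour 8 (an assumption prompted by the 6 to 8 hours in Section 8.3.1), with even use, mean stay 3 days and at least 1 day. Power is then about 58%, 58% and 56% for mg per day at c = 0.2, 0.3 and 0.5, and 47%, 38% and 25% for the stay total. For the first 24 hours the effect is 6.65 × 16/24 = 4.43 mg, power is 37%, and 80% would need 116 per arm. That window would also miss most of the 8-hour versus 96-hour contrast behind the trial, so it is suggested only as a sensitivity analysis.

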8.2 Blinding

All patients will be blinded to the treatment groups as they will receive the one-time treatment while under general anesthesia in the operating room.

All study staff will be blinded to the treatment groups, except those staff involved in assigning treatment groups. Access to the randomization code will be strictly controlled. The study blind will be broken on completion of the clinical study and after the study database has been locked.

Investigators will be blinded to the medical treatment groups - Standard Bupivacaine and Liposomal Bupivacaine. As Standard Bupivacaine is clear and Liposomal Bupivacaine is milky white, obscuring over-wraps will be placed over syringe. See Section 8.3-8.3.2 for more information.

During the study, the blind may be broken only in emergencies when knowledge of the patient's treatment group is necessary for further patient management. If this occurs, the investigator will contact the study staff involved in assigning treatment groups, and the blind will be broken. When possible, the investigator should discuss the emergency with the Medical Monitor prior to unblinding.

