15.5 Interim Analysis

There will be interim reviews conducted by the DMC for the purpose of monitoring study conduct and assessing patient safety at 1/3 and 2/3 goal enrollment. Blinding will be maintained. An O'Brien-Fleming alpha spending function with symmetric stopping boundaries for benefit and harm will be utilized. If the stopping boundaries have been reached (absolute value of z-value >3), the data will be unblinded for review and the trial will be terminated. Finally, there also will be consideration of terminating trial if there is consensus of futility.

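### Section 15.3 lets a transformation, a Mann-Whitney test or a six-covariate regression take over from the default t-test on undefined triggers, without saying which result then governs

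*Combined protocol and SAP*

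**What the plan says.** Section 15.3 opens with the default: "Student's t-test will be used to assess the means of the cumulative total of in-hospital oral morphine equivalents". The synopsis names only that test. Section 15.3 then gives two conditional departures.

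- Normality: "If this assumption is not met, transformation or nonparametric tests (Mann-Whitney U test) will be used". No diagnostic or cut-off is given, no transformation is named, and nothing decides between transforming and ranking.
- Balance: because there are only 40 subjects per group, "it is possible that we do not achieve effective randomization". The consequence is: "If this occurs, we will utilize linear regression adjusting for age, sex, race, comorbidity, diagnosis, and procedure performed". No measure of imbalance or threshold is given. The section does not say whether the regression replaces the t-test or sits beside it, or what happens if both conditions arise.

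On timing, section 15 states: "Prior to the analysis of the final study data, a detailed Statistical Analysis Plan (SAP) will be written". Section 8.2 states: "The study blind will be broken on completion of the clinical study and after the study database has been locked". Section 15.5 provides for interim reviews at 1/3 and 2/3 of enrolment: "If the stopping boundaries have been reached (absolute value of z-value >3), the data will be unblinded for review". It names neither the endpoint nor the test behind that z.

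The planning figures are per day: "The mean daily in-hospital usage of opioids is 35mg morphine equivalents with standard deviation of 12mg" (section 15.6). Section 15.3 tests the total over the stay.

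**The concern.** The text permits at least four routes to the primary p-value: a raw t-test, a test on a transformed scale, a rank test and an adjusted mean difference. They also address different quantities, so a switch changes the question as well as the p-value.

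The balance trigger is the weaker of the two, because it has no natural criterion. Allocation is by permuted blocks (sections 8.1 and 15.6). Chance differences in baseline variables are expected under that scheme and do not show that randomisation failed. Someone must therefore judge whether the condition is met, and nothing in the plan prevents that judgement from being made with the results in view. At stake is the primary conclusion in those trials where the permitted analyses disagree.

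**Working it through.** **Inputs.** From section 15.6: mean 35 mg/day, SD 12 mg, reduction 19%, so 0.19 × 35 = 6.65 mg/day; 80 subjects at 1:1, so 40 per arm; two-sided alpha 0.05. From section 15.3: six covariates. Assumed, because the documents give no figures: covariate R² of 0.10 to 0.25, independent covariates, and a normal daily outcome except where stated. The documents give no SD for the stay total, so the main figures are on the daily scale.

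**1. The plan's own power.** SE = 12 × √(2/40) = 2.683. Noncentrality = 6.65/2.683 = 2.478 on 78 df. Power is 68.7%, against the stated 80%. That mismatch is a separate matter; 68.7% is simply the baseline for step 5.

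**2. How often a plausible balance rule would fire.** If ineffective randomisation meant any of six independent covariates at p<0.05, the chance under correct randomisation is 1 − 0.95⁶ = 0.265, or about 26%.

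**3. How often the choice matters.** Share of simulated trials in which the t-test and the adjusted model fall on opposite sides of p=0.05, under the planned effect (40,000 trials per setting):

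| Covariates | R² 0.10 | R² 0.25 |
|---|---|---|
| 4 | 10.9% | 16.5% |
| 6 | 11.8% | 16.8% |

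With no true effect the share is about 3–5%.

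**4. Type I error.** Each test used alone gives 4.9–5.1%. A mechanical rule (adjust if any of six covariates has p<0.05, otherwise use the t-test) gives 4.5–4.7%. Reporting the smaller p-value of the t-test and the adjusted model gives about 6.4–7.5%, which is an upper bound for that pair.

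**5. Power of one fixed adjusted model.** With k covariate df, SE = 12 × √(1−R²) × √(2/40) × √(77/(77−k)) on 78−k df. For k = 4:

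| R² | SE | 6.65/SE | Power |
|---|---|---|---|
| 0 | 2.756 | 2.413 | 66.3% |
| 0.10 | 2.614 | 2.544 | 70.9% |
| 0.25 | 2.387 | 2.786 | 78.5% |

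Break-even with the unadjusted 68.7% is at R² of about 0.05.

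**6. Cost of staying on the mg scale.** If stay totals were log-normal (assumed, with the effect set for 80% power on the log scale), the power of the raw t-test against Mann-Whitney is 78% v 78% at CV 0.34, 74% v 78% at CV 0.6, and 70% v 77% at CV 0.8.

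**The case against.** The strongest reply is that the plan is less open than it looks. The t-test is the default in both the synopsis and section 15.3, so a governing test exists until a trigger fires. A detailed SAP is promised before the final analysis, and the blind holds until database lock, so the ordinary course is a SAP written blind. The DMC charter (section 14.1) also has the committee finalise the statistical methods for its reports at a meeting before any enrolment. The synopsis and section 15.5 describe the interim reviews as being for safety and conduct. Finally, the 11–17% applies only if the planned effect is real, and it depends on an assumed R².

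Most of this is right, and it limits the point. A reader might infer that the interim stopping decision is left open because comparative z-values would precede any choice of method. The documents do not support that: the charter provides a step for fixing the interim method before data exist, and section 15.5 ties z to no endpoint. What remains is narrower. The charter refers to methods specified in the protocol, which does not settle the choice. The charter also gives the committee effectiveness monitoring, and the SAP is due only before the final analysis. An efficacy comparison by arm could therefore precede the SAP.

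The promise of a SAP does not supply the missing criteria or say which result governs after a switch.

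**Conclusion.** The point holds as a gap in specification that should be closed. Two data-driven switches lack a criterion, an order and a governing result. The choice between the t-test and the adjusted model would change the primary conclusion in about 11–17% of trials under the planned effect and about 3–5% under the null, on the daily scale with R² assumed at 0.10 to 0.25.

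Two stronger readings should be resisted. One is that section 15.3 inflates type I error as written. Conditional adjustment under a fixed rule stays near 5%, and the rise to about 6.4–7.5% requires picking the smaller p-value, which the plan does not propose. The other is that adjustment is needed to recover power. The documents give no R², and four covariates lose power if R² is below about 0.05. The reason for the change is to have one fixed test.

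**What to change.** In the SAP, finalised before any efficacy comparison by arm (including any efficacy z under section 15.5) and at the latest before unblinding:

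- Name one primary linear model, with arm plus a short fixed set of covariates from the section 15.3 list, fitted whatever the observed balance. Age, sex, diagnosis and procedure would serve, with the coding stated. The particular set is the sponsor's choice.
- Delete the conditional wording on randomisation and the normality switch.
- Analyse the outcome in mg, and reconcile the stay total of section 15.3 with the daily figure of section 15.6.
- Report the unadjusted t-test and the Mann-Whitney test as sensitivity analyses that cannot replace the primary result.

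A log scale is not a safe substitute. Opioids are given as needed (section 7.1), so zero totals are possible. With an assumed 5% of zeros, a mean total of 90 mg and CV 0.6, a t-test on log(total + 1) had about 32% power against 66–67% for the raw t-test.

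The cost is SAP wording and no new data collection. The downsides are a few degrees of freedom (66.3% power against 68.7% if R² is 0) and some loss on the mg scale if totals are skewed (step 6).

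A separate free improvement concerns the SF-8, which is collected at Visits 1 and 3 and assessed as a change (sections 5.2, 9.1.6 and 15.4). Analyse the Visit 3 score by ANCOVA with the Visit 1 score as covariate, in place of a t-test on change. With equal variances the variance ratio is (1+ρ)/2: 0.65 at ρ = 0.3 and 0.75 at ρ = 0.5 (both assumed). This is a gain in efficiency; a t-test on change is valid.
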